### **Our study will examine secondary factors which encompass physical and psychosocial measures (Hypotheses 1B).**

*Service Dogs and Healthcare Utilization*: Popular belief holds that pet owners, especially dog owners, enjoy better health than their peers who do not own pets. Indeed, exposure to animals, especially dogs, has been shown to have positive physiological consequences, leading to decreased health care utilization. Simply stroking a dog decreases physiological arousal, including lowering blood pressure, decreasing heart rate and slowing respiration, and increasing finger temperature. Anderson et al. examined a large sample of healthy clinic patients (n=5,741) in Australia and found that compared to individuals who did not own pets, pet owners (primarily dog owners) also had lower triglyceride and cholesterol level, in addition to lower blood pressure levels. In general, a national probability sample from Australia found pet owners to have better health and decreased health care utilization as measured by number of doctor visits and medication use. Individuals who had companion animals visited the physician less often and used less medication according to other studies. If touching a dog can have such a remarkable impact, what are the long-term effects of human-animal interaction, specifically partnership with an SD?

Very little data exists regarding health status and health care utilization of SD partners. A cross-sectional study of SDs partners (n=57, response rate 90 percent) conducted by Lane et al., found participants to report increased self-perceived health after receiving a SD, though most had

degenerative illnesses. Fairman et al.'s cross-sectional survey reported SD partners used 2.1 less hours of paid and 5.9 less hours of unpaid assistance each week after receipt of their SDs. The estimated cost savings due to decreased paid assistance hours was \$600 per year. Based on the previously mentioned estimate of 16,000 SD users in the United States, this represents a potential savings of \$9.6 million per year due to decreased reliance on paid assistance. Limitations in these studies include cross-sectional design resulting in recall bias of previous events and controversial studies.

Individuals with PTSD are significantly correlated with increased health care utilization, work disability, lower socioeconomic status, morbidity, and mortality. Moreover, requiring assistance in activities of daily living (ADL) reliably predicts nursing home admissions, and as a result, has influenced state and federal healthcare policy. Limitations in ADL and instrumental activities of living IADL serve as eligibility criteria for public and private disability benefits as well as outcomes by which clinicians and researchers evaluate the efficacy of their interventions. **The proposed study will examine healthcare utilization in relation to having a service dog (Hypotheses 2A and 2B).**

#### *Significance of Research*

VA hospitals nationwide are integrating service dogs into treatment plans for disabled Veterans. However, with the training of SDs taking up to nine months and costs estimated at \$23,000 per SD, the utilization of SDs as adjunct to mental health treatment is in need of investigation. This study will be the first to assess the impact of highly trained SDs on the psychological, behavioral and social functioning of a Veteran population.

The idea that the presence of animals can produce calming effects in humans is commonly cited in areas of stress reduction. Also, relevant to internalizing disorders are unconditional positive regard as well as acceptance, which may help to promote an increased sense of self-efficacy and trust in others, as well as reduced feelings of rejection and inadequacy. Studies of the ability of animals to alter perceptions of social desirability and to increase positive social interactions between strangers have been uniformly positive. It has also been cited that pets provide feelings of companionship, security, and of being loved. It is thought that this occurs because animals provide an opportunity for emotional investment that is free of negative evaluation and not subject to feelings of rejection. Finally, companion animals may promote the formation of secure attachment relations with another living being and thereby contributing to one's basic sense of trust.

To date, there have been no long-term follow-up studies of the impact or efficacy of animal-assisted interventions. Although some have attempted to determine if changes in behavior could be observed beyond the context of the intervention (generally school and home) the results are conflicting.

When considered alongside the large numbers of anecdotal statements attesting to the power of animals to hasten the building of rapport between patient and therapist, these findings have important healthcare implications. If the presence of an animal can make the therapist appear less threatening, it seems reasonable to believe that some patients would achieve a greater sense of comfort more quickly and remain in therapy. In addition to enhancing the patient's perception of

the healthcare provider, the presence of an animal provides a benign, external topic of conversation on which to focus, which may further hasten and enhance the development of a working alliance. Given that compliance and retention in treatment, as well as treatment outcomes, may be strongly related to the quality of the therapeutic relationship, this particular aspect of animal-assisted interventions merits urgent investigation.

The use of dogs as companions and an adjunct to current mental health treatment is quite promising. Professionally trained SDs can assist Veterans find misplaced items due to cognitive memory loss (e.g., wallet, cell phone, keys); perform functions to assist with PTSD symptoms (e.g., alert bark, safety check of rooms, position self between stranger and owner in large crowds); result in fewer doctor contacts; and serve as catalysts or mediators of human social interactions and may expedite the rapport-building process between patient and therapist. Not only can a dog assist Veterans to meet physical challenges and proceed in therapy, but they can be utilized to overcome a lot of the mental instability that they feel.

### **Preliminary Studies**

The principal investigator (PI) has completed several pilot studies on SDs. An overview of the studies is provided below. NOTE: PI name changed in 2009 from [name] to [name].

*Wheelchair Assistance Dog –Merit Review # D3078R* was completed expanding the pilot work of the PI. For sake of space, information on the pilot studies has not been included. This prospective study compared four groups over an 18-month period: those who had recently received a SD and those waiting to receive a SD, those who had pets and those who did not have a pet. All participants completed questionnaires at baseline (prior to receipt of dog), and at 3, 9, 12 and 18 months (post receipt of dog for the SD group). The questionnaires covered demographics, socioeconomics, health care utilization, and psychosocial characteristics (e.g., self-esteem, affect) as well as functional outcomes.

There were a total of 186 participants enrolled in the Merit Review study. Of these participants, 123 completed all five collection points over the 18-months of the study and 14 were withdrawn or dropped out by missing more than one questionnaire. The mean age was  $46.1 \pm 12.2$  years, having their disability/diagnosis for  $25.3 \pm 15.6$  years. Forty percent of the subjects had progressive disabilities ranging from multiple sclerosis to amyotrophic lateral sclerosis and 60% had non-progressive disorders such as cerebral palsy and spinal cord injury. The population was also comprised of 83.9% Caucasian and 62.9% female. 31.4% were actively employed. At baseline, groups were comparable in all outcomes. After all follow-up was completed, the only significant difference in psychosocial outcomes was found between groups with respect to depression ( $p=.047$ ). No other measures were significantly different between the groups for other psychosocial variables [fatigue ( $p=.342$ ), loneliness ( $p=.656$ ), positive affect ( $p=.088$ ), negative affect ( $p=.313$ ) or self-esteem ( $p=.129$ )]. Significant differences were also seen the occupational component of the Craig Handicap Assessment and Reporting Technique CHART tool ( $=0.025$ ). In both findings, those who were on the waiting list to receive the service dog were significantly more depressed and less functional (CHART) than the other groups.

*Epidemiology of Service Dogs* was a second study funded by VISN 4 aimed to: 1) describe the population partnered with SDs based on the characteristics of the individual, 2) determine the association between of length of SD partnership and the individual characteristics and 3)

Dogs and PTSD: V11: 11.26.14

compare the characteristics described above between individuals who have yet to receive a SD and individuals already utilizing a SD. Identical information was collected as described for previous study.

Because of the large population that we recruited, we completed a secondary data analysis to examine sub populations. Of specific interest, was to determine if those individuals who required human assistance would benefit more from a SD. Of the 375 individuals who contributed data, 89% were Caucasian, 66.4% were females with an average of 45.7 years old ( $\pm$  12.9) and a mean duration of injury or disability equaling 23.4 years ( $\pm$  14.9). One hundred sixty-four individuals (43.7%) owned SDs.

Significant differences were found between the two groups (those who had SDs and those who did not) with respect to functioning and community participation as measured by the CHART. People who had SDs had more cognitive independence ( $p=0.00$ ), were more able to participate in and maintain customary social relationships ( $p=0.00$ ) and had better mobility than their counterparts. Those partnered with SDs had higher positive affect scores ( $p=0.000$ ), but reported taking fewer medications than those individuals without SDs ( $p=0.000$ ). Individuals with SDs reported using more hours of paid assistance for instrumental activities of daily living (IADLs) – such as running errands ( $p=0.000$ ), than those without SDs. This suggests that if an individual requires functional help, SDs may be of benefit.

*Hearing and Service Dogs: An alternative assistive technology:* A service directed project (#B3089R) was subsequently funded to examine SDs and hearing dogs (HD) as an alternative to assistive technology (AT). A combination of questionnaires and observation was completed to assess types of assistive technology including healthcare utilization and caregiver help questions as well as specific questions related to SDs.

Cost issues associated with AT: People partnered with a SD pay on average \$75 per month to care for their dog while the SD comparison group also paid \$75 per month for their AT needs. Although not statistically different, SD partners pay about \$188 per month for their AT devices ( $p=0.16$ ). However, these differences in costs associated with service dog versus AT devices is a function of disability and race ( $p=0.159$ ). In addition, participants partnered with a SD were asked if they had to make accommodations to their environment. Eighty-eight percent made changes to their surroundings and 74% had to pay for these changes out of pocket with the median total cost being \$400 and a range of \$10 to \$6,600. HD partners paid about \$100 per month to care for their dog in addition to an average of \$74 per month for the AT needs. In comparison, HD controls pay about \$145 per month for their AT needs. No significant differences were observed between these monthly costs ( $p=0.01$ ). When the HD individuals were partnered with their dog, 62% ( $n=8$ ) made changes to their environment and 75% of these individuals paid for their accommodations. The range of cost for changes was \$75 to \$2000 with a median cost of \$250.

Assistance dogs specific questions: For those individuals partnered with assistance dogs, additional questions were asked that were specific to the reliability and satisfaction of their dogs. For those with SDs, 90% reported being very satisfied with their dogs overall. Similarly, 82% were very satisfied with the agency from which they obtained their dogs, and 86% were very

satisfied with the training the agency provided for using their dogs. Eighty-five percent of the SD partners received follow-up training with their dogs and of these individuals, 81% were extremely satisfied with this training. Overall, about 86% of the population felt their SD was very reliable.

For those who were partnered with HD, 69% stated they were very satisfied with their dog, 77% stated they were very satisfied with the dog agency as well as the training they provided to work with the dog. Seventy-nine percent of the population partnered with HDs received follow-up training of their dogs, with 67% being very satisfied with this training. Eighty-five percent of the HD respondents rated the reliability of their HD greater than an eight on a scale of 1-10, with 10 being most satisfied ( $\geq 9$ ).

Very little data exists regarding changes in health care utilization of individuals partnered with assistance dogs. This study found that those with dogs were less likely to have visits to the doctor and spend less time than their counterparts. Although number of visits is a crude measure of healthcare utilization it still represents a potential that the impact assistance dogs may have on their partner. Research conducted on pets in general has shown that contact with them may actually decrease the occurrence of disease as well as decrease stress and anxiety. Within this respect, the dog is not only benefiting the individual from a technology perspective but also a psychosocial perspective.

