### **Research Design and Methods**

#### *Design*

This 3-year, mixed methods modified, non-randomized trial will follow individuals for two years. Due to the inability to recruit veterans interested in participating in a control (no dog) group, this group has been eliminated going forward with the study. The study will examine the influence of SDs by assessing the longitudinal change in mental health assessment over time among veterans who have PTSD. The group will consist of individuals partnered with SDs. Following initial screening for inclusion criteria, including criteria set by dog vendors, subjects who are eligible will receive a SD. This study will measure changes over time in the primary outcome of mental health. Additional outcomes in psychosocial health and healthcare utilization will be included. Recruits successfully completing the screening process will be placed on a vendor's waiting list to receive a SD upon the dog's completion of training. Recruits who do not meet all criteria, including vendor criteria, will be ineligible to participate..

Data will be collected at baseline and at 3, 6, 9, 12, 18 and 24 months for individuals with service dogs. For those awaiting service dogs, repeated assessments will occur every 3 months until obtaining a SD. Once baseline data has been collected for 24 months, assessments will occur every 6 months until the Veteran is paired with a SD. Baseline data will include detailed information on the characteristics of the participants, their mental health, psychosocial well-being, socioeconomic and healthcare utilization characteristics. As we want to obtain information regarding the changes in health and wellbeing over time, a prospective study will permit this type of comparison.

*Sample:* The study will use a convenience sample of VHA patients who are currently in treatment for PTSD. We have chosen to use these criteria as a safety measure for the veteran and the dogs. At this time, there are currently 600 veterans receiving care at James A. Haley VAMC for PTSD, with an estimated 25 new veterans seen in the clinic per week. We are confident that an adequate number of Veterans will be recruited for the study. We will monitor recruitment and retention numbers on a monthly basis. The use of additional VA hospitals as a potential source for recruitment is the contingency plan should we be unable to meet enrollment numbers.

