*Screening Visit:* Once a Veteran has agreed to participate in the study, they will be asked to participate in a screening visit. Once the informed consent process is finalized, eligibility criteria will be confirmed. A review of CPRS records will be conducted by the study team to verify the Veteran truly meets all criteria. At this time, if all criteria are met, all baseline questionnaires will be completed and field notes taken. For safety reasons, Veterans who have children younger than 10 years of age in the home for more than 8 hours per day, one day per week or more will be excluded from the study. After 20 dogs have been placed without incident, this criterion will be revisited to potentially allow these Veterans to participate.

- The study team will perform a home evaluation visit prior to referring Veterans to a vendor. This visit will be to ensure the environment is safe and suitable for a

dog. A home environment checklist has been developed and will guide the study team in assessing the environment. An information sheet that provides details to Veterans regarding why and how the home visit will be conducted will be provided to Veterans when Informed Consent is obtained. During the visit, the team will check to see that there is an area for a dog to exercise, relieve itself, sleep, as well as making sure hazardous plants or chemicals are not within reach of a dog. All family members that will be living in the home will be expected to meet with the study team to ensure they understand the study requirements and are on board with bringing a dog into the home. If any issues are identified by the study team during the home evaluation the Veteran will have 3 weeks to fix the issues and reschedule a follow up home evaluation visit. If during the follow up home evaluation the study team determines that the issues are not fully resolved the Veteran will have one additional week to remedy the issues and reschedule a final home evaluation. If the issues remain unresolved the Veteran will be withdrawn from the study. Once the home evaluation has been approved the Veteran will be provided with contact information for the vendor. The Veteran will be instructed to contact the vendor and will be placed on the waiting list. The Veteran will be encouraged to review home owner/rental insurance policy to include a dog and be required to obtain a license for their service dog per local laws.

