Training of SDs for a specific individual takes time, and immediate placement of a dog with a Veteran most likely will not occur. Thus, baseline data collection will occur at the time of consent and every three months until the dog becomes available for the Veteran. If a Veteran completes 24 months of observation and is still not paired with a dog, assessments will continue every 6 months until a dog becomes available. If the Veteran is not been paired by 48 months they will be withdrawn from the study. Through observations and questionnaires we will ask the Veteran about how they feel, their mood, and their quality of life. During the waiting period, Veterans will be required to take an education course related to dog care and responsibility of dog ownership. This course will be provided by the study team and will be online through CITI or via paper copy. A paper copy of the Education Modules in the course will be provided to Veterans as a reference. Course content will cover all aspects of Service Dog ownership including grooming, health maintenance, and financial responsibility. A competency test will be given at the end of the course to ensure Veterans understand the material. If the Veteran fails to pass the test with a score of 80% or better, remedial training will be given by the study team and the test will be re-taken until passed. A Veteran Guide for Veterinary Care information sheet will be provided at this time as well. This Guide will contain information about health maintenance and when to take the dog to the veterinarian.

Once the study team receives word from a vendor that a SD is about ready for pairing, the Veteran and vendor will have an opportunity to talk to ensure that an appropriate match will be made. When the dog is ready, the Veteran will be required to travel to the vendor location. Travel may be by air or car, depending on the vendor location and considering the Veteran's preference when possible. If a Veteran drives their personal vehicle, he/she will be reimbursed at the government mileage rate upon completion of training and return home. Vendor staff will make travel and lodging arrangements for the Veteran. Lodging, air travel, and meals will be paid for by the vendor during the pairing (per Federal regulations) and reimbursed by VA per the SOW. The pairing process may vary by vendor and can last from one to three weeks.

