**Hypothesis 1B:** *Improvements in secondary factors of physical, psychosocial, and socioeconomic variables will be seen in the SD group over time.* Variables within the physical (medication, comorbidities), psychosocial (affect, depression, loneliness) and socioeconomics (healthcare utilization) will be compared over time and will be assessed for each variable of interest using a repeated measures mixed model for dependent variable (DV) scored a continuous scale and generalized estimating equations (GEE) models for DV variables scored as a categorical. Dependent variables for all models will be scale or subscale scores. The within-participants variable will be the score at each time point (baseline, 3, 9, 12, 18 and 24 months). If significant differences exist at baseline for any confounding variables, that factor will be controlled for in the analysis. We expect to show improvements in all characteristics over the course of the study.

We will also complete a multivariate logistic regression to determine predictors of success (dichotomized higher scores after 18 months on function and participation). We expect that improvements in psychosocial factors (e.g, community participation) will result. We expect the data to be normally distributed; therefore, linear regression will be used. Results from the previous hypotheses (1B) will be used to determine which predictor variables are entered into the regression model; any variable with a  $p$ -value less than 0.10 will be considered. Highly related variables will be entered into the model separately. Any confounders significant at baseline will

Dogs and PTSD: V11: 11.26.14

be controlled for in the models. In addition, we will repeat the multivariate logistic regression analysis described above with group (SD vs. control) as a primary fixed variable. We expect that subjects paired with a SD will demonstrate increased improvement in psychosocial factors.

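### With the control group dropped, change over time stands in for the service-dog effect, yet the baseline is undefined and no planned analysis uses the repeated pre-pairing scores

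*Combined protocol and SAP*

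**What the plan says.** - **One group.** The Design section states: "Due to the inability to recruit veterans interested in participating in a control (no dog) group, this group has been eliminated going forward". The hypotheses are worded as improvement over time in Veterans partnered with a dog.
- **Scores before pairing.** At the screening visit, after consent: "At this time, if all criteria are met, all baseline questionnaires will be completed and field notes taken". Only after an approved home evaluation does the next step follow: "The Veteran will be instructed to contact the vendor and will be placed on the waiting list". The same section says that "baseline data collection will occur at the time of consent and every three months until the dog becomes available for the Veteran", and Design adds: "Once baseline data has been collected for 24 months, assessments will occur every 6 months until the Veteran is paired with a SD". A Veteran still unpaired at 48 months is withdrawn.
- **Concurrent treatment.** The inclusion criteria and the Intervention paragraph require active PTSD treatment throughout the study.
- **Analysis.** Hypothesis 1A uses a repeated-measures mixed model with the baseline PCL score as covariate and does not say which score that is. Hypothesis 1B states: "The within-participants variable will be the score at each time point (baseline, 3, 9, 12, 18 and 24 months". Hypotheses 2A and 2B specify a within-subject repeated-measures analysis and list no time points.
- **Earlier study.** Preliminary Studies reports, for wheelchair service dogs, that "those who were on the waiting list to receive the service dog were significantly more depressed and less functional (CHART) than the other groups".

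**The concern.** Without a concurrent comparison, anything that moves scores between the reference assessment and follow-up becomes part of the apparent dog effect. Two sources are visible in the protocol. One is ongoing PTSD treatment, which can shift PCL, PHQ-9, sleep and quality of life without a dog. The other is the wait, which may be long and, on the earlier study's evidence, might itself affect mood and function. Either could push the result in either direction.

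Aim 1 is to determine the impact of service dogs, and that conclusion rests on this contrast. The study collects a series of no-dog scores on the same Veterans that could inform the trend, but the analysis section does not say how they are used. It also does not say which of them is the baseline, and that choice decides how much non-dog change enters the contrast.

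**Working it through.** SD below means standard deviation, not service dog.

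**1. The plan's own figure.** The Sample section gives about 100% power for dog group status (alpha 5%, effect size 5.54, effect SD 0.47, first-order autocorrelation 0.80, at least 5 assessments). A noncentral F test with two groups (assumed, since the number is not stated) gives power 1.00 at effect size 5.54. With 0.47 read as the standardised effect, it gives at least 0.9996 for a total of 130 or more. The figure reproduces, but it is for a group contrast that the single-group design no longer contains.

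**2. Scores collected and scores used.** Months 0 to 24 in steps of 3 give 9 assessments. Months 30, 36 and 42 make 12, and a month-48 assessment makes 13. Since withdrawal falls at month 48, a paired Veteran would normally have at most 12. These are ceilings; no expected wait is stated. The models name one baseline.

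**3. What the choice of baseline does.** Assume treatment drift of 0.1 SD per year and no dog effect, and look 24 months after pairing.
- From a score taken at pairing: 0.1 × 24/12 = 0.2 SD.
- From the consent score after a 12-month wait: 0.1 × 36/12 = 0.3 SD.
- From the consent score after a 48-month wait: 0.1 × 72/12 = 0.6 SD.

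The drift rate is assumed. The example shows only that the undefined choice matters.

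**4. How small a shift would look significant.** Inputs: 220 enrolled less 15% (33) leaves 187. Correlation is 0.80 at best, or 0.80^6 = 0.262 if the stated autocorrelation is carried over the six intervals to month 24. The standard error of a paired change, in SD units, is sqrt(2(1 − ρ)/187).
- ρ = 0.80: sqrt(0.400/187) = 0.046.
- ρ = 0.262: sqrt(1.476/187) = 0.089.

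Chance of two-sided p < 0.05 with no dog effect:

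| Assumed non-dog shift | ρ = 0.262 | ρ = 0.80 |
|---|---|---|
| 0.1 SD | 20% | 58% |
| 0.2 SD | 61% | 99% |
| 0.3 SD | 92% | 100% |

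The shift detected with 80% power is (1.960 + 0.842) × standard error, or 0.13 to 0.25 SD. A paired test is a simplification of the planned mixed model.

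**5. What the earlier study can bear.** Its groups were comparable at baseline, and the difference is reported after follow-up. Depression (p = .047) was the only significant one of six psychosocial measures listed. Six independent tests at 0.05 give 1 − 0.95^6 = 26% chance of at least one false positive. The functional difference was in the occupational component of CHART only.

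**6. What modelling cannot do.** Suppose distress rises 0.2 SD over a 12-month wait and vanishes at pairing, with no dog effect. Change from the last waiting score is 0.2 SD, and from the consent score 0. Departure from the Veteran's projected waiting trend, 24 months after pairing, is 0.2 × 36/12 = 0.6 SD. Extrapolating the individual trend makes the bias worse.

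**The case against.** A reader might infer that the reference scores are all taken on the vendor waiting list, are depressed by waiting, and that relief from waiting will therefore be reported as a dog benefit. The documents do not support this. The first baseline is completed at the screening visit, before waiting-list entry, and only the repeats are taken while waiting. The earlier study concerned wheelchair users, found no difference at its own baseline, and gives p-values without effect sizes. It reports nothing on sleep or quality of life.

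Three further objections have force.
- Waiting ends exactly when the dog arrives, so no model can separate relief from waiting, or expectancy, from the dog. This stands in full. The waiting series helps with drift over time, not with relief.
- The month list under Hypothesis 1B also omits month 6, which Design collects, so it is poor evidence that waiting scores were deliberately excluded. This is fair, but Hypotheses 1A, 2A and 2B give those scores no role either.
- Loss of the control group is openly stated, and the protocol plans to abstract records from at least a year earlier to look at trends and to track PTSD visits and therapies. This is relevant to treatment drift, but no model term is attached to it.

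The shift sizes in the table are assumptions, and sensitivity to small shifts is common to any single-group pre-post study of this size.

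**Conclusion.** The concern holds in a limited form. The baseline is undefined, the repeated pre-pairing scores have no stated place in any analysis, and with one group under continuing treatment, non-dog change could be read as a service-dog benefit or could mask one. This follows from the design and does not depend on the earlier study, which only makes a waiting effect plausible.

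Neither the size nor the direction of any such change can be taken from the documents. The 20% to 99% range for shifts of 0.1 to 0.2 SD rests on 187 completers, correlations from 0.262 to 0.80, a paired test, and a shift that is assumed. The protocol elsewhere expects 200 completers; at 200, the 0.2 SD range is 64% to 99%, so the message does not change.

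**What to change.** In the analysis text for Hypotheses 1A and 1B:

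1. State which pre-pairing score is the baseline, and report change from both the consent score and the last score before pairing.
2. Add a prespecified supportive mixed model for PCL, PHQ-9, PSQI, SF12 and CIQ that uses every pre-pairing assessment. Include time since consent, and pairing as a time-varying term with level and slope before and after pairing. Staggered pairing dates then help to separate drift from pairing, provided that length of wait is not itself related to a Veteran's course. Avoid long extrapolation of individual waiting trends.
3. State that relief from waiting and expectancy coincide with pairing and cannot be separated from it by any model. Describe results as change after pairing, not as the causal impact of the dog.

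The cost is analysis-plan wording and modest extra analysis, with no new data. Intervals will be wider than for simple pre-post change, and Veterans with short waits will add little information on the pre-pairing trend.
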